2.4.3.3 Cemiplimab exposure

The cemiplimab dose information will be assessed by the following:

- Total number of cycles started.
- Number of cycles started by patient.
- Duration of cemiplimab exposure (or time on-treatment) (in weeks) is defined depending on the cemiplimab administration schedule as follows:
 - Q2W cemiplimab administration: [date of last dose of cemiplimab + 14 days - date of first dose of cemiplimab]/7,
 - Q4W cemiplimab administration: [date of last dose of cemiplimab + 28 days - date of first dose of cemiplimab]/7.
- Actual dose (mg): for a given cycle and day of administration.
- Cumulative dose (mg): the cumulative dose is the sum of all actual cemiplimab doses.

- ADI in mg/week: defined as the cumulative dose (in mg) divided by the duration of cemiplimab exposure (in weeks).
- RDI in %:

$$100 \times \frac{\text{ADI (mg/week)}}{\text{Planned Dose Intensity (mg/week)}}$$

Planned dose intensities in mg/week is 125 mg/week for Q2W schedule, and 62.5 mg/week for Q4W schedule.

The total number of cycles started, number of cycles started by patients as a quantitative variable and by category (ie, number [%] of patients receiving at least 1 cycle, at least 2 cycles, etc), duration of cemiplimab exposure, cumulative dose, ADI and RDI will be summarized by descriptive statistics.

The following variables will be derived to describe dose delays/modifications:

- Dose delay (within a cycle, only applicable to Q2W schedule): A dose is deemed as delayed if the actual start date of the infusion – theoretical start date of an infusion is >2 days for Q2W administration. Dose delay does not apply to the first infusion of each cycle.
- Infusion interruption: An infusion will be considered to be interrupted (as collected on CRF) if the cemiplimab administration is stopped during an infusion before it is completed regardless of whether it is further restarted or not.
- Dose omission: a dose is considered omitted if the dose is not administered for the scheduled visit and there are positive dose(s) afterwards.

Dose delayed/modification will be analyzed at the patient, cycle and the total number of cemiplimab administration levels as follows:

- Patient level (number of all treated patients will be used for % calculation):
 - Number (%) of patients with at least 1 dose delay,
 - Number (%) of patients with at least 1 dose omission,
 - Number (%) of patients with a least 1 infusion interrupted:
 - Number (%) of patients with a least 1 infusion interrupted and re-started,
 - Number (%) of patients with a least 1 infusion interrupted and not re-started,
 - Number (%) of patients with at least 2 infusions interrupted.
- Infusion level
 - Total number of infusions (used for % calculation for this section),
 - Number (%) of infusions interrupted:
 - Number (%) of infusions interrupted and re-started,
 - Number (%) of infusions interrupted and not re-started,

- Number (%) of infusions interrupted more than once,
- Number of infusion interrupted at (with % calculated using the total number of infusions interrupted): 1st infusion, 2nd infusion, subsequent infusions,
- Time from infusion start to first interruption in minutes (quantitative and qualitative: 5-10, 11-30, 31- 60, 61-90, 91-120, >120).

Duration of cemiplimab infusion (in hours) is defined as the time from the start (date/time) of cemiplimab infusion to the end (date/time) of cemiplimab infusion in the same visit. It will be summarized for first and subsequent infusions.

2.4.4 Analyses of efficacy endpoints

All analyses described in this section are applicable to the Phase 2 part of the study only. For Phase 1, a listing of response data including duration of response on the all treated population will be provided instead of summary table.

In Phase 2, all primary, secondary and exploratory analyses will be performed using the randomized population in Phase 2.

The cutoff date for the primary analysis of ORR will be 6 months after the date of the first dose of the last patient. In this analysis, hypothesis test(s) will be performed ([Section 2.4.4.1](#)).

Final analysis cutoff date for OS analysis and updated analysis of ORR and other secondary endpoints will be approximately 12 months after the date of the first dose of the last patient.

An interim analysis of response rate (including confirmed and unconfirmed responses) will be conducted when the first 15 randomized patients in each arm have completed 2 cycles of treatment or definitively discontinued the treatment. A combination arm will be stopped early for futility ([Section 3](#)).

2.4.4.1 Analysis of primary efficacy endpoint(s)

The ORR will be summarized by treatment arms with descriptive statistics. A 95% two-sided confidence interval(s) will be computed using Clopper-Pearson. BOR will also be summarized descriptively.

The Fisher's exact test will be performed to compare the ORR in control arm vs each of the combination arm, using a 1-sided significance level of 0.10 with Hochberg adjustment (at time of primary analysis of ORR; ie, cutoff date 6 months after last patient first dose). If the maximum p-value (of two p-values) is less than 0.1, the null hypothesis for both combination arms will be rejected; else if minimal p-value is less than 0.05, the null hypothesis will be rejected for this corresponding arm only. If only one combination arm is continued after the interim analysis in addition to the control arm, then ORR will be tested using an 1-sided significant level of 0.05.

ORR and BOR will also be summarized descriptively for subgroups variable defined in [Table 4](#).

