7 SELECTION OF PATIENTS

7.1 NUMBER OF PATIENTS

Approximately 108 to 138 patients.

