9.1.5 Immunogenicity

It is of utmost importance to collect all blood samples at the specified times and according to the specifications for collection, storage, and shipment as defined in a separate laboratory manual.

Samples missed or lost, for any reason should be recorded. Actual dates and times of blood collection should be recorded in the eCRF. The dates and times of drug administration should also be precisely recorded.

The cemiplimab and isatuximab ADA sampling times for blood collection can be found in the PK Flow Chart ([Section 1.2](#) and [Section 1.3](#)).

- For cemiplimab during treatment phase, samples for immunogenicity assessment are to be collected every third Cycle from C5 (ie, on D1 of C5, C8, C11, C14, etc) till the last study treatment. In response to AEs of special interest, such as anaphylaxis or hypersensitivity, ADA samples closer to the event may be collected, based on the judgment of the Investigator and/or medical monitor. If isatuximab is stopped and cemiplimab treatment continues, cemiplimab ADA samples should be collected as planned per PK/PD flow-chart.
- For isatuximab, samples for immunogenicity assessment are to be collected during the course of the study. However, collection can be stopped earlier based on the updated knowledge of isatuximab immunogenicity (note that collection was indeed interrupted at cut-off date of primary efficacy analysis 6 months after LPI). At FU 90 (± 7) days after last IMP administration if ADA is positive or inconclusive no further ADA will be sampled. The ADA results will be communicated to investigational sites on an ongoing basis.

Bioanalytical methods used for immunogenicity assessment are summarized in [Table 7](#).

Table 7 - Bioanalytical methods for immune response assessment

Analyte	ANTI ISATUXIMAB ANTIBODY	ANTI CEMIPLIMAB ANTIBODY
Matrix	Plasma	Serum
Analytical technique	PandA method	Non-quantitative bridging immunoassay
Lower Limit of Quantification	Not applicable	Not applicable
Site of bioanalysis	Covance Harrogate (UK)	Regeneron Pharmaceuticals, Inc. (Tarrytown, NY)

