13.4.4.1 Analysis of primary efficacy endpoint

The ORR will be summarized by treatment arms/cohort with descriptive statistics. A 95% two-sided confidence interval(s) will be computed using Clopper-Pearson.

For Phase 2 randomization part of the study, the Fisher's exact test will be performed to compare the ORR in control arm vs each of the combination arm, using a 1-sided significance level of 0.10 with Hochberg adjustment, (at time of primary analysis of ORR; ie, cutoff date 6 months after last patient first dose). If the maximum p-value (of two p-values) is less than 0.1, the null hypothesis for both combination arms will be rejected; else if minimal p-value is less than 0.05, the null hypothesis will be reject for this corresponding arm only. If only one combination arm is continued in addition to the control arm, then ORR will be tested using a 1-sided significant level of 0.05.

Subgroup analyses of BOR will be performed including but not limited to the following variables listed:

- Age: <70 years versus ≥ 70 years.
- Number of previous lines of therapy: ≤ 3 vs >3 .

- ISS staging at study entry: I vs II vs III.
- High risk cytogenetic (such as del (17), t (4:14) or t (14:16) abnormality): Yes vs No.
- Baseline creatinine clearance : <60 mL/min vs \geq 60 mL/min.
- Refractory to prior anticancer treatments (eg, IMiD, PI): Yes vs No.
- PD-L1 level at baseline: \geq 50% vs <50%

For Phase 1 all treated population, a listing of response data will be provided.

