Based on updated analysis of primary endpoint (overall response rate [ORR]) planned six months after last patient in (LPI) and other secondary endpoints (including overall survival [OS]) performed at the planned cutoff date 1 year after LPI, the addition to cemiplimab to SAR650984 only resulted in marginal additive efficacy. No safety concerns were observed during periodic Data Monitoring Committee (DMC) review. No further efficacy data collection at longer follow-up will be performed. Per DMC recommendation, the final OS analysis planned at 24 months after LPI will not be performed and the follow-up will stop after the extended safety period of 90 days after last study treatment dose. Participants under treatment will continue to be treated as long as they benefit from it.

A risk of hepatitis reactivation has been identified in the SAR650984 Investigator's Brochure Edition 11 (30-Apr-2020).

Protocol amendment summary of changes table

Section # and Name	Description of Change	Brief Rationale
Clinical trial summary; 1.1 Study flowchart; 1.2.2 ISATUXIMAB QW/Q2W + CEMIPILIMAB Q2W (DL1) - Treatment phase: Cycle 2 and beyond (Sparse sampling); 1.2.3 ISATUXIMAB QW/Q2W + CEMIPILIMAB Q2W (DL1) - End of treatment and follow-up periods; 1.3.2 ISATUXIMAB QW/Q2W + CEMIPILIMAB Q4W (DL-1) - Treatment phase: Cycle 3 and beyond (Sparse sampling); 1.3.3 ISATUXIMAB QW/Q2W + CEMIPILIMAB Q4W (DL-1) - End of treatment and follow-up periods; 6.6.1 Duration of study participation for each patient; 6.6.2 Determination of end of clinical trial (all patients); 9.2.1 Primary endpoint (Phase 2 only); 12.4.4.2 Further follow-up visits until 12 months after LPI; 12.4.5 Post OS study cut-off date	Follow-up procedures after the extended safety period of 90 days after last study treatment dose will not be performed anymore after amended protocol 05 approval. The final OS analysis planned at 24 months after LPI will not be performed. Patients benefiting from study treatment may continue receiving treatment beyond amended protocol 05 implementation.	The addition to cemiplimab to SAR650984 only resulted in marginal additive efficacy. No safety concerns were observed during periodic DMC review. No further efficacy data collection at longer follow-up will be performed per DMC recommendation.

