1.3 DETERMINATION OF SAMPLE SIZE

In Phase 1 part, the objective is to determine the recommended Phase 2 Dose (RP2D) based on DLT occurrence. The actual sample size will depend on DLTs observed and number of dose levels actually explored. It is anticipated that 3 to 18 DLT-evaluable patients will be treated in the Phase 1 part of the study.

In Phase 2 randomization part, the objective is to evaluate the efficacy and safety of the combination therapy. Assuming ORR=20% in control arm (isa alone arm) and ORR=50% in combination arms, using Fisher's exact test to compare the ORR in control vs combination arms and an overall 1-sided type I error of 5% for each combination arm, 35 patients per arm is required to achieve a 79% power for each combination arm. EAST 6.0 was used in the sample size calculation. The total expected number of patients treated in Phase 2 randomization part is 105.

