3 INTERIM ANALYSIS

For Phase 2 part, a formal interim analysis of response rate (including confirmed and unconfirmed responses) will be performed when the first 15 randomized patients in each arm completed 2 cycles of treatment or permanently discontinue treatment. The purpose of the analysis is to stop combination arm early for futility.

The analysis will include the first 15 randomized patients from each arm in the ITT population. Given the observed response rate (including confirmed and unconfirmed responses) from each combination arm, and assuming the numbers of response follow binomial distribution with response rate=20% in control arm, and 50% in combination arm for the remaining 20 patients in each arm, the conditional power can be calculated based on 1-sided Fisher's exact test at 0.05 significance level (for each combination arm vs. control arm separately) at the end of the trial. If the conditional power is <30% for a combination arm, the arm will be stopped early for futility. The detailed decision rule of whether to continue or stop the arm is included in [Appendix B](#). R-code for calculating conditional power is included in [Appendix C](#).

The analysis will include the following parameters/analyses (defined in [Section 2](#)): response rate (including confirmed and unconfirmed responses), demographics and baseline characteristics, prior or concomitant medication, AEs (TEAE, death, SAE, TEAE leading to discontinuation and IR), laboratory variables (abnormality of hematological and chemistry test), PK NCA after first administration and ADA based on available data.

In addition, formal safety review by data monitoring committee (DMC) are planned approximately every 3 months to regularly monitor unblinded patient safety data (all meetings), unblinded efficacy data (except the 1st DMC meeting) and quality of trial conduct. More details on formal safety reviews and on interim analyses are given in the DMC charter.

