5 SOFTWARE DOCUMENTATION

All summaries and statistical analyses, except for biomarker analysis, will be generated using SAS® Version 9.4 or higher. Biomarker analyses will be performed using R software Version 3.4.0 or above.

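### Does Fisher's exact test waste power in the ORR comparison, so that a more powerful exact test should replace it?

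*SAP*

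**What the plan says.** The plan uses one test throughout.

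- **Sample size.** SAP 1.3 and protocol 13.1 assume an ORR of 20% on control and 50% on combination, with a one-sided 5% Fisher test for each combination arm. They conclude that "35 patients per arm is required to achieve a 79% power for each combination arm".
- **Final analysis.** SAP 2.4.4.1 states that Fisher's "exact test will be performed to compare the ORR in control arm vs each of the combination arm", and protocol 13.4.4.1 says the same. Both apply Hochberg's procedure at a one-sided 0.10: "If the maximum p-value (of two p-values) is less than 0.1, the null hypothesis for both combination arms will be rejected". Otherwise the arm with the smaller p-value succeeds alone if that value is below 0.05. If only one combination arm continues past the interim, it is tested at 0.05.
- **Interim.** SAP 3 and protocol 13.5 compute conditional power for the same Fisher test at 0.05, and SAP Appendix C codes it. "If the conditional power is <30% for a combination arm, the arm will be stopped early for futility".

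Neither document mentions an unconditional exact test.

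**The concern.** Fisher's test conditions on the total number of responders in the two arms compared. The design fixes the arm sizes but not that total. Conditioning leaves few attainable p-values, so the test usually rejects less often under the null than its nominal level allows.

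Boschloo's test orders the tables by Fisher's p-value but takes the worst case over the unknown common ORR. It rejects every table that Fisher rejects, and some more, while still holding the level. In a trial planned with only 79% power per comparison, several points of power at no cost in patients look like something the plan should not have left unused. At stake would be a missed effect: an arm truly at 50% would fail about one time in five in a single comparison under Fisher, against about one in seven under Boschloo.

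**Working it through.** **Inputs.** 35 patients per arm, 20% against 50%, thresholds 0.05 and 0.10 one-sided (SAP 1.3 and 2.4.4.1). Futility is judged at 15 patients per arm with a 30% cut-off (SAP 3).

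**Step 1: the plan's own figure.** With c control and t combination responders, Fisher's one-sided p-value is the hypergeometric tail P(T ≥ t | c + t) with 35 patients in each arm. Writing b for the binomial probability,

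power = Σ_c Σ_t b(c; 35, 0.20) · b(t; 35, 0.50) · 1{p(c,t) < 0.05}.

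Summing over all 36 × 36 outcomes gives 0.7914. The stated 79% is reproduced.

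**Step 2: is Fisher conservative here?** Set both arms to a common rate π in the same sum and take the maximum over π. The maximum size is 0.0361 at the 0.05 threshold and 0.0659 at 0.10. At π = 20% the 0.05-level test has size 0.0263. So it is conservative, and therefore valid.

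**Step 3: Boschloo's test.** Its p-value is the maximum over π of P{Fisher p ≤ observed Fisher p}. At 35 against 35 this amounts to rejecting when Fisher's p is below 0.0725 (for 0.05) or below 0.1412 (for 0.10). Maximum size is 0.0498 and 0.0959, so it is valid too. With 7/35 control responders, success at 0.05 needs 14/35 (Fisher p 0.0583, Boschloo p 0.0364), where Fisher needs 15/35.

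**Step 4: both tests under the plan's decision rule.** For Hochberg, the sum runs over all 36³ three-arm outcomes with the shared control. Control is at 20% throughout.

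| Situation | Fisher | Boschloo |
|---|---|---|
| Single comparison at 0.05, 50%: power | 79.1% | 85.1% |
| Hochberg, both arms 50%: per-arm power | 86.3% | 90.1% |
| Same, present futility rule applied | 85.6% | 89.2% |
| Hochberg, one arm 50%, other 20%: power of the active arm | 79.2% | 85.3% |
| Hochberg, both arms 40%: per-arm power | 57.7% | 66.1% |
| All arms 20%: any false claim | 5.1% | 7.6% |
| Any false claim, maximum over a common ORR | 6.6% | 9.3% |
| Null arm beside a 50% arm: false claim | 5.9% | 8.9% |

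The futility row assumes that interim responses carry forward to the final analysis.

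Under the planning alternative the gain is 90.1 − 86.3 = 3.8 points per arm. With one active arm it is 85.3 − 79.2 = 6.1 points. The price with all arms at 20% is a rise by a factor of 7.6 / 5.1 = 1.5 in false claims. Every error rate in the table stays below the 10% that the plan allots.

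**Step 5: the interim rule.** Today the conditional power describes the test that will be used at the end. With Boschloo as the final test and the futility rule left as it is, an arm one responder behind a control count of 1 to 5 would still be stopped. Its conditional power is 19% to 29% under Fisher but 30% to 37% under Boschloo. If the test in the Appendix C function were swapped at the same 30%, the chance of stopping an ineffective arm (20% against 20%) would fall from 40.9% to 25.0%. Either way something else in the design has to give.

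**Step 6: timing.** A primary test may be changed only before unblinded results are known. SAP 3 gives the DMC unblinded efficacy data from its second meeting on. Protocol 9.1.5, on isatuximab ADA sampling, notes that "collection was indeed interrupted at cut-off date of primary efficacy analysis 6 months after LPI". The rationale for amended protocol 05 in Appendix K opens: "Based on updated analysis of primary endpoint (overall response rate [ORR]) planned six months after last patient in (LPI"; it goes on to report that cemiplimab added little efficacy. The ORR result was therefore known by then.

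**The case for a change.** The best case for a change is that the gain is real and was there to be had when the SAP was written. Both tests are exact and hold the same nominal level. Boschloo's rejection region contains Fisher's, and no patients are added. Fisher's test would need 42 patients per arm to first reach 85% power in the single comparison, 7 more per arm than planned. If the sponsor accepts a one-sided 10% overall error, using about half of it at the assumed control rate can be called wasteful.

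The arithmetic stands, and so does the lesson for a future design. It does not follow that this plan is deficient. The unused error is not lost: it is a lower actual false-positive rate, which a sponsor may prefer when the nominal level is already as lenient as one-sided 10%. Under the plan's alternative and its actual decision rule, per-arm power is already 86.3%, above the 79% stated for a single comparison.

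The change is also less simple than it looks. The Boschloo cut-offs hold only at 35 against 35: the 0.0725 cut-off gives a maximum size of 0.0571 at 34 against 34. The protocol synopsis, protocol 13.1 and 13.5 and SAP 1.3 and 3 would all have to be reworked. SAP 5 ("All summaries and statistical analyses, except for biomarker analysis, will be generated using SAS") means validated SAS programming of a less familiar test.

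**Conclusion.** The concern does not hold. Fisher's test is valid, the 79% is right, and sizing, final test and futility rule agree with one another. Boschloo's test would buy 3.8 points of per-arm power under the plan's alternative and about 6 points with one active or one continuing arm. In return, the chance of any false claim with all arms at 20% would rise by half, from 5.1% to 7.6%. That is a choice between two valid tests on which competent statisticians differ.

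For this trial the choice is also closed: ORR had been analysed by amended protocol 05, so Fisher must stay primary, and Boschloo could appear only as a labelled post hoc sensitivity analysis. The figures assume 35 analysed patients per arm, a control ORR of 20% and, for the 86.3% and 90.1%, both combination arms truly at 50%.

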2.4.4.2 Analyses of secondary efficacy endpoints

No hypothesis testing will be performed on secondary efficacy endpoints. The following analyses will be performed:

- CBR: will be summarized with descriptive statistics.
- VGPR or above rate: will be summarized with descriptive statistics.
- DOR: Kaplan-Meier estimates of the 25th, 50th and 75th percentiles including the 95% confidence interval as well as Kaplan-Meier curves will be provided for patients who achieve a response \geq PR. DOR will be also summarized with statistics in the subset of patients with BOR \geq PR.
- PFS and OS: PFS and OS will be analyzed using the Kaplan-Meier method. The Kaplan-Meier estimates of the 25th, 50th and 75th percentiles and their associated 95% confidence interval will be computed. The Kaplan-Meier curves will be plotted.
- DFU and TTR will be summarized with descriptive statistics. Best percent change in paraprotein will be displayed in a waterfall plot. In the waterfall plot, patients with BOR of \geq PR will have negative percentage change. The patients will be ordered from highest positive change to smallest negative change. Percent change $>100\%$ will be displayed as 100% increases. A swimmer plot of time on treatment (ie, duration of exposure) will also be provided. The patients will be ordered by BOR and duration of exposure. Patients with the best BOR and longest duration will be presented at the top of the plot.

A listing of response data will be provided for the randomized population and second listing will be provided for patients who are ADA positive ([Section 2.1.6](#)), and will include the following variables: high risk status, number of prior lines of anti-myeloma treatment, selected prior treatments given (alkylating agent, IMid, PI, mAb), duration of exposure (weeks), reason for treatment discontinuation, measurable paraprotein at baseline, best percent change in paraprotein, best overall response, date of first response \geq PR, date of first disease progression/last disease assessment, indication of progressive disease, time to first response and DOR.

A listing of best percent change in % plasma cell in bone marrow biopsy will be provided and will include the following variables: measurable paraprotein at baseline, best percent change in paraprotein, BOR, baseline plasma cells count; post baseline plasma cells count and best percent change in plasma cells count.

Number (%) of patients with MRD negative will be provided. This may be replaced by a listing if the number of MRD negative patient is small (≤ 5).

Subgroup analyses for secondary endpoints may be performed if relevant.

